7.4. Summary of Human Clinical Experience with EXPAREL

The EXPAREL clinical development program assessed the efficacy and safety across a wide range of body regions and applications, investigating its use in the management of acute pain when administered as a peripheral nerve block for regional analgesia, and as a field block for local analgesia. Pacira has conducted 31 clinical studies (13 Phase 1, 7 Phase 2, and 11 Phase 3). Across the 31 completed studies in the clinical program, safety data were collected on 3644 subjects (2141 subjects received EXPAREL, 850 subjects received IR bupivacaine alone, and 653 subjects received placebo).

Across these studies, a total of 2141 adult human subjects received EXPAREL at doses ranging from 9 to 665 mg and by various routes, including field block, peripheral nerve block, subcutaneous, and epidural routes of administration. EXPAREL was well tolerated and had a

favourable safety profile when administered as a field block or as an interscalene brachial plexus nerve block in varying degrees of vascularity in subjects undergoing various surgical procedures. The frequency and types of events are consistent with the profile of other local anaesthetics.

At doses up to 665 mg of EXPAREL, no central nervous system or cardiovascular system AEs observed with high doses of bupivacaine HCl solution have been observed with EXPAREL. Two thorough QTc studies have been conducted; EXPAREL did not cause significant QTc prolongation even at the highest dose evaluated.

Across all studies, the types and the incidence rates of treatment-emergent AEs (TEAEs) were similar between the EXPAREL All Doses group (all doses combined) and the bupivacaine HCl group. The incidence rate for each of the three most common TEAEs (nausea, constipation, and vomiting) was lower in the EXPAREL All Doses group than in the bupivacaine HCl group.

In terms of efficacy, three positive Phase 3 studies (402-C-316, 402-C-317, 402-C-331) demonstrated statistically significant improvements in pain intensity scores compared to placebo or bupivacaine HCl in the postoperative period when administered as a field block (infiltration). All three studies also showed a statistically significant reduction compared to placebo or bupivacaine in total opioid consumption; Studies 316, 317 and 331 additionally show a significantly higher percentage of opioid-free patients and a significantly longer time to first opioid use compared to placebo or IR bupivacaine.

An analysis was performed to compare the incidence of opioid-related AEs between the EXPAREL and bupivacaine HCl groups in all bupivacaine-controlled, parallel-group infiltration studies in adults (SIMPLE TKA [total knee arthroplasty] 311, SKY0402-C-208, SIMPLE Hemorrhoidectomy 312, SKY0402-C-209, SKY0402-C-207, SKY0402-C-201, and SIMPLE Breast Augmentation 315). There was a statistically significantly lower incidence of opioid-related AEs in the EXPAREL <266 mg group compared to the bupivacaine HCl group till 72 hours post dose. This was consistent with the statistically significantly lower total postoperative consumption of opioids in the EXPAREL \leq 266 mg group till 72 hours post dose. Fewer subjects in the EXPAREL ≤266 mg group had at least one opioid-related AE compared to the bupivacaine HCl group (25.6% versus 45.6%; p<0.0001). The total opioid medication administered (adjusted geometric mean) till 72 hours post dose was statistically significantly lower in the EXPAREL \leq 266 mg group (7.94 mg) compared to the bupivacaine HCl group (15.84 mg); p<0.0001. The EXPAREL >266 mg group did not show a statistically significant advantage favoring EXPAREL; the mean (standard deviation [SD]) of the average number of opioid-related AEs per subject was 0.58 (0.522), and the total opioid medication administered (adjusted geometric mean) till 72 hours post dose was 22.82 mg in the EXPAREL >266 mg group.

Please see the EXPAREL Full Prescribing Information for safety information regarding the use of EXPAREL for the treatment of postsurgical pain in the setting of infiltration.

Please refer to the Investigator's Brochure for additional information regarding the completed studies.

7.5. Postmarketing Exposure in Adults and Children

As of May-2018, more than 4 million patients have received EXPAREL in the postmarketing setting. While EXPAREL is not approved for use in patients less than 18 years of age, there is evidence that it has been widely used off-label in pediatric cases.

The Premier PerspectiveTM Database (PPD) is the largest inpatient drug utilization database in the US and contains de-identified hospital chargemaster data from approximately 600 hospitals, which accounts for approximately 15% of all hospitalizations nationwide (McDonald 2013). Recent inquiries into the PPD between 01-Jan-2011 and 31-Mar- 2017 found that it contains data for 2461 patients aged less than 18 years who had been exposed to EXPAREL in both inpatient and outpatient settings, including 1796 patients between 6 and <17 years of age.

In addition, The Cleveland Clinic (Cleveland, Ohio) currently uses EXPAREL off-label as part of its postsurgical multimodal analgesia for patients under the age of 18 years across several surgical procedures. A retrospective chart analysis is being conducted to evaluate the safety profile and clinical benefit of EXPAREL in this setting.

8. **OBJECTIVES**

8.1. Primary Objective

The primary objective is to evaluate the pharmacokinetics (PK) of EXPAREL in pediatric subjects aged 6 to less than 17 years undergoing surgery.

8.2. Secondary Objectives

The secondary objective is to evaluate the safety of EXPAREL in pediatric subjects aged 6 to less than 17 years undergoing surgery.

9. OVERALL STUDY DESIGN AND PLAN

9.1. Overall Study Design and Plan

This is a two-part study to evaluate the PK and safety of EXPAREL in pediatric subjects aged 6 to less than 17 years. Part 1 will evaluate PK and safety in subjects aged 6 to less than 17 years, while Part 2 will assess safety in subjects aged 6 to less than 17 years.

In Part 1, subject enrollment will be conducted in parallel to include the older age group (12 to <17 years old; Group 1) and the younger age group (6 to <12 years old; Group 2).

Subject enrollment for Part 2 (of each group) will commence upon complete enrollment of Part 1 (of that group). In Part 2, subject enrollment will be conducted in parallel to include the older age group (12 to <17 years old; Group 1) and the younger age group (6 to <12 years old; Group 2).

Dosing of EXPAREL will be based on body weight, with a starting dose of 4 mg/kg (maximum 266 mg).

Γ	Surgery Type, Dose, and Number of Subjects [n]			
	Part 1 (PK and Safety)	Part 2 (Safety)		
Group 1 (subjects aged 12 to	Spine Surgery	Spine Surgery		
<17 years)	EXPAREL 4 mg/kg [15] bupivacaine HCl 2 mg/kg [15]	EXPAREL 4 mg/kg [15] bupivacaine HCl 2 mg/kg [15]		
Group 2 (subjects aged 6 to	Spine or Cardiac Surgery	Spine or Cardiac Surgery		
<12 years)	EXPAREL 4 mg/kg [15]	EXPAREL 4 mg/kg [15]		

Part 1 (Pharmacokinetics- PK) - Subjects aged 6 to less than 17 years

Part 1 is a multicenter, randomized, open-label study in 45 subjects aged 6 to less than 17 years of age undergoing spine or cardiac surgeries. There will be two treatment groups: Group 1 will include subjects aged 12 to less than 17 years of age, while Group 2 will include subjects aged 6 to less than 12 years of age.

Part 1, Group 1, is an active-controlled, open-labeled, PK evaluation study in subjects aged 12 to less than 17 years undergoing spine surgery. The active comparator will be bupivacaine HCl. The sample size is a total of 30 subjects (15 subjects per treatment group). Subjects will be randomized 1:1 to receive either a single dose of EXPAREL 4 mg/kg (maximum 266 mg) or bupivacaine HCl 2 mg/kg (not exceeding a maximum bupivacaine HCl dose of 175 mg total) intraoperatively at the end of surgery via local infiltration.

Part 1, Group 2, is a single-arm (EXPAREL 4 mg/kg), open-labeled, PK evaluation study in subjects aged 6 to less than 12 years undergoing spine or cardiac surgery. The sample size is a total of 15 subjects. Subjects will receive a single dose of EXPAREL 4 mg/kg (maximum 266 mg) intraoperatively at the end of surgery via local infiltration.

The total sample size for Part 1 is 45 subjects aged 6 to less than 17 years, with 30 subjects in Group 1 and 15 subjects in Group 2.

Part 2 (Safety) - Subjects aged 6 to less than 17 years

Part 2 is a multicenter, randomized, open-label, safety study in 45 subjects aged 6 to less than 17 years undergoing spine or cardiac surgeries. There will be two treatment groups: Group 1 will include subjects aged 12 to less than 17 years, while Group 2 will include subjects aged 6 to less than 12 years.

Part 2, Group 1, is an active-controlled, open-labeled, safety evaluation study in subjects aged 12 to less than 17 years undergoing spine surgery. The active comparator will be bupivacaine HCl. The sample size is a total of 30 subjects (15 subjects per treatment group). Subjects will be randomized 1:1 to receive either a single dose of EXPAREL 4 mg/kg (maximum 266 mg) or bupivacaine HCl 2 mg/kg (not exceeding a maximum bupivacaine HCl dose of 175 mg total) intraoperatively at the end of surgery via local infiltration.

Part 2, Group 2, is a single-arm (EXPAREL 4 mg/kg), open-labeled study in subjects aged 6 to less than 12 years undergoing spine or cardiac surgery. The sample size is a total of 15 subjects. Subjects will receive a single dose of EXPAREL 4 mg/kg (maximum 266 mg) intraoperatively at the end of surgery via local infiltration.

The total sample size for Part 2 is 45 subjects aged 6 to less than 17 years, with 30 subjects in Group 1 and 15 subjects in Group 2.

The overall safety assessments will include all 45 subjects from Part 1 and all 45 subjects from Part 2, with a total of 90 subjects.

Subjects will be screened within 30 days prior to study drug administration. During the screening visit, subjects will be assessed for past or present neurologic, cardiac, and general

medical conditions that, in the opinion of the investigator, would preclude them from study participation. After the ICF is signed by the subject's legal guardian and written assent is provided by the subject (if capable), medical history, surgical history, physical examination, 12-lead electrocardiogram (ECG), vital sign measurements, neurological assessment, clinical laboratory tests (hematology, chemistry, and urinalysis), pain intensity score, urine pregnancy test for females of childbearing potential, urine drug screen and alcohol breath test will be conducted.

On Day 1, eligible subjects will receive the study drug intraoperatively at the end of surgery via local infiltration to produce local analgesia. Use of intraoperative opioids, acetaminophen, ketorolac, or other NSAIDs, will be permitted in accordance with the study site's standard of care.

Avoid additional use of local anesthetics within 96 hours following the administration EXPAREL.

There is no required length of stay in the hospital; subjects may be discharged based on the medical judgment of the treating physician. For subjects discharged from the hospital before all protocol-specified assessments till 96 hours are completed, a nurse will perform follow-up visits at the subject's home to perform the required postsurgical assessments and collect PK samples till 96 hours.

A follow-up phone call will be scheduled for all subjects on Day 7. For the assessment of AEs, a final follow-up visit will be made on Day 30 to all subjects who would have received the study drug.

Postsurgical Pain Management

Use of postsurgical pain medication in cases of insufficient analgesia will be permitted according to the institution's standard of care. The investigator must record all postsurgical pain management medications provided to the subjects till the hospital discharge.

Avoid additional use of local anesthetics within 96 hours following the administration EXPAREL.

Postsurgical Assessments

Postsurgical assessments to be conducted till 96 hours include pain intensity using the 11-point NRS-R (Appendix 1) for subjects aged 12 to less than years and the Color Analog Scale (CAS; Appendix 2) for subjects aged 6 to less than 12 years; neurological assessment (Appendix 3); clinical laboratory tests (Appendix 4); and vital signs.

AEs will be recorded from the time the ICF is signed/assent is given till Day 30.

In case a cardiac or neurological AE of special interest (AESI) or serious AE (SAE) occurs during the study, if the investigator or medical monitor considers that the event may be related to study treatment or suggests the possible occurrence of local anesthetic systemic toxicity (LAST; with or without the need for treatment [e.g., intralipids]), or if a plausible etiology for the event cannot be found, an unscheduled PK blood sample must be collected and a 12-lead ECG, vital signs, and clinical laboratory tests (hematology and complete metabolic profile [CMP]) according to the study site's standard of care may be conducted. See Section 13.1.7 and Appendix 6 for additional information on handling of AESIs. Cardiac or neurological AEs that do not meet one of these three criteria for AESI should be reported as described in Section 14.1 and captured in the database as an AE.

Cardiac AESIs include chest pain, abnormal/irregular heart rate, and shortness of breath requiring intervention. Neurologic AESIs include seizure, altered mental status/altered sensorium, rigidity, dysarthria, tremors, tinnitus, visual disturbance, and severe or worsening dizziness (see below). Additionally, the following events may be of special interest if they persist or occur beyond 72 hours post dose: dizziness, hyperesthesia, muscular twitching, and tingling/paresthesia.

Dizziness will be assessed as mild, moderate, or severe based on the National Cancer Institute (NCI) Common Terminology Criteria for Adverse Events (CTCAE) Version 5.0. Mild dizziness is defined as mild unsteadiness or sensation of movement; moderate dizziness is defined as moderate unsteadiness or sensation of movement limiting instrumental activities of daily living (ADL); and severe dizziness is defined as severe unsteadiness or sensation of movement that limits self-care ADLs. Dizziness will be captured as an AESI if it is severe or worsens or persist beyond 72 hours post dose.

Pharmacokinetic Assessment (Part 1 only)

A population PK sampling scheme will be used to limit the number of blood draws for each individual subject. On Day 1, eligible subjects will be assigned to one of the two PK sampling groups shown below based on surgery type (Table 2). A total of 8 blood samples will be collected from each subject at the specific time windows shown for the determination of bupivacaine plasma concentrations. Having two PK sampling sequences for spine and cardiac surgeries will help to guard against clustering of PK samples.

Surgery	PK Sample Timing (Based on the End of Study Drug Administration)							
Туре	Sample 1	Sample 2	Sample 3	Sample 4	Sample 5	Sample 6	Sample 7	Sample 8
Spine	15±5 min	30±5 min	45±5 min	1-1.25 h	2-3 h	10-18 h	24-36 h	42-60 h
Cardiac	15±5 min	30±5 min	45±5 min	1-1.25 h	15-25 h	30-40 h	45-55 h	64-72 h

Table 2: PK Sample Collection

h: hour; min: minutes; PK: pharmacokinetic.

These sampling time points will not only characterize overall PK of bupivacaine from EXPAREL, but will also characterize the PK of immediate release bupivacaine and thoroughly characterize the early peak for both treatments.

Note that a new needle stick may not be necessary for each blood draw. The subject may be fitted with a peripheral venous line at the discretion of the investigator to facilitate the collection of blood for PK assessment.

In the situation where PK blood draws and other assessments coincide or occur at about the same time, the blood draw for PK analysis must be conducted first, and the pain intensity assessment conducted second, as applicable, followed by other assessments.

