In the situation where PK blood draws and other assessments coincide or occur at about the same time, the blood draw for PK analysis must be conducted first, and the pain intensity assessment conducted second, as applicable, followed by any other assessments.

1 ECG abnormalities that are clinically significant should be recorded as AEs. May also conduct a 12-lead ECG if a subject experiences an AESI (i.e., cardiac AE or neurological AE), or an SAE; see footnote 7.

2 A baseline 12-lead ECG must be recorded prior to surgery and may be performed either at the screening visit or in the preoperative holding area on Day 1.

3 May also conduct clinical laboratory tests if a subject experiences an AESI or an SAE; see footnote 7.

4 Vital signs (temperature, resting heart rate, respiratory rate, oxygen saturation and blood pressure) will be measured after the subject has rested in a supine position for at least 5 minutes. May also measure vital signs if a subject experiences an AESI (i.e., cardiac AE or neurological AE), or an SAE; see footnote 7.

5 Pain intensity will be measured using the 11-point NRS-R for subjects aged 12 to less than 17 years (Appendix 1) and CAS for subjects aged 6 to less than 12 years (Appendix 2). The preoperative pain intensity assessment should be conducted immediately prior to each administration of postoperative opioid pain management medication till 96 hours. If a subject is too anesthetized at the time of a scheduled pain intensity assessment, the assessment should be skipped.

6 Instruct subject to discontinue prohibited medications. Record date/time of all medications starting at least 30 days prior to study drug administration till 96 hours after study drug administration. Record medications administered for treatment of an AE till Day 30.

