13.1.7. Adverse Events of Special Interest

All AEs will be recorded from the time the ICF is signed/assent is given till Day 30. In case a cardiac or neurological AE of special interest (AESI) or serious AE (SAE) occurs during the study, if the investigator or medical monitor considers that the event may be related to study treatment or suggests the possible occurrence of local anesthetic systemic toxicity (LAST; with or without the need for treatment [e.g., intralipids]), or if a plausible etiology for the event cannot be found, an unscheduled PK blood sample must be collected and a 12-lead ECG, vital signs, and clinical laboratory tests (hematology and complete metabolic profile [CMP]) according to the study site's standard of care may be conducted. See Appendix 6 for additional information on handling of AESIs.

Cardiac AESIs include chest pain, abnormal/irregular heart rate, and shortness of breath requiring intervention. Neurologic AESIs include seizure, altered mental status/altered sensorium, rigidity, dysarthria, tremors, tinnitus, visual disturbance, and severe or worsening dizziness (see below). Additionally, the following events may be of special interest if they persist or occur beyond 72 hours post dose: dizziness, hyperesthesia, muscular twitching, and tingling/paresthesia.

Dizziness will be assessed as mild, moderate, or severe based on the NCI CTCAE Version 5.0. Mild dizziness is defined as mild unsteadiness or sensation of movement; moderate dizziness is defined as moderate unsteadiness or sensation of movement limiting instrumental ADL; and severe dizziness is defined as severe unsteadiness or sensation of movement that limits self-care ADLs. Dizziness will be captured as an AESI if it is severe or worsens or persist beyond 72 hours post dose. Cardiac or neurological AEs that do not meet one of these three criteria for AESI should be reported as described in Section 14.1 and captured in the database as an AE.

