The study protocol specified that if a cardiac or neurological AE of special interest (AESI) or serious AE (SAE) occurs during the study, if the investigator or medical monitor considers that the event may be related to study treatment or suggests the possible occurrence of local anesthetic systemic toxicity (LAST; with or without the need for treatment [e.g., intralipids]), or if a plausible etiology for the event cannot be found, an unscheduled PK blood sample must be collected and a 12-lead ECG, vital signs, and clinical laboratory tests (hematology and complete metabolic profile [CMP]) according to the study site's standard of care may be conducted. Cardiac and neurological AEs that do not meet one of these three criteria for AESI should be reported and captured in the database as an AE.

Cardiac AESIs include chest pain, abnormal/irregular heart rate, and shortness of breath requiring intervention. Neurologic AESIs include seizure, altered mental status/altered sensorium, rigidity, dysarthria, tremors, tinnitus, visual disturbance, and severe or worsening dizziness (see below). Additionally, the following events may be of special interest if they persist or occur beyond 72 hours post dose: dizziness, hyperesthesia, muscular twitching, and tingling/paresthesia.

Dizziness will be assessed as mild, moderate, or severe based on the National Cancer Institute-Common Terminology Criteria for Adverse Events (NCI-CTCAE) Version 5.0. Mild dizziness is defined as mild

unsteadiness or sensation of movement; moderate dizziness is defined as moderate unsteadiness or sensation of movement limiting instrumental activities of daily living (ADL); and severe dizziness is defined as severe unsteadiness or sensation of movement that limits self-care ADLs. Dizziness will be captured as an AESI if it is severe or worsens or persist beyond 72 hours post dose.

4. **DEFINITIONS**

Study Day

If the date of the event is on or after the date of the end of study drug administration, Study Day is calculated as the date of the event minus the date of the end of study drug administration plus one (1). If the date of the event is before the date of the end of study drug administration, Study Day is the date of the event minus the date of the end of study drug administration.

Treatment-emergent Adverse Events

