Note to programmer: Replace "TREATMENT" with "SURGERY TYPE", followed by "Spine Surgery" or "Cardiac Surgery".

Listing 16.2-17.2.1.1.1: Treatment-emergent Adverse Events (Group 1: 12 to <17 years) - All Subjects

Listing 16.2-17.2.1.1.2: Treatment-emergent Adverse Events (Group 2: 6 to < 12 years) - All Subjects

Listing 16.2-17.2.2.1.1: Treatment-emergent Study Drug Related Adverse Events (Group 1: 12 to <17 years) -All Subjects Listing 16.2-17.2.2.1.2: Treatment-emergent Study Drug Related Adverse Events (Group 2: 6 to < 12 years) -All Subjects Note to programmer: Replace "TREATMENT" with "SURGERY TYPE", followed by "Spine Surgery" or "Cardiac Surgery". Listing 16.2-17.3.1.1: All Serious Adverse Events (Group 1: 12 to <17 years) - All Subjects Listing 16.2-17.3.1.2: All Serious Adverse Events (Group 2: 6 to < 12 years) - All Subjects Note to programmer: Replace "TREATMENT" with "SURGERY TYPE", followed by "Spine Surgery" or "Cardiac Surgery". Listing 16.2-17.4.1.1.1: Treatment-emergent Serious Adverse Events (Group 1: 12 to <17 years) - All Subjects Listing 16.2-17.4.1.1.2: Treatment-emergent Serious Adverse Events (Group 2: 6 to < 12 years) - All Subjects Note to programmer: Replace "TREATMENT" with "SURGERY TYPE", followed by "Spine Surgery" or "Cardiac Surgerv". Listing 16.2-17.4.2.1.1: Treatment-emergent Study Drug Related Serious Adverse Events (Group 1: 12 to <17 years) - All Subjects Listing 16.2-17.4.2.1.2: Treatment-emergent Study Drug Related Serious Adverse Events (Group 2: 6 to < 12 years) - All Subjects **Note to programmer:** Replace "TREATMENT" with "SURGERY TYPE", followed by "Spine Surgery" or "Cardiac Surgery". Listing 16.2-17.5.1.1.1: Treatment-emergent Adverse Events of Special Interest, as Reported by Investigators (Group 1: 12 to <17 years) - All Subjects Listing 16.2-17.5.1.1.2: Treatment-emergent Adverse Events of Special Interest, as Reported by Investigators (Group 2: 6 to < 12 years) - All Subjects Note to programmer: Replace "TREATMENT" with "SURGERY TYPE", followed by "Spine Surgery" or "Cardiac Surgery". For these tables, use the CRF checkbox to identify AEs of Special Interest. Listing 16.2-17.5.2.1.1: Treatment-emergent Study Drug Related Adverse Events of Special Interest (Group 1: 12 to <17 years) - All Subjects Listing 16.2-17.5.2.1.2: Treatment-emergent Study Drug Related Adverse Events of Special Interest (Group 2: 6 to < 12 years) - All Subjects

Pacira Pharmaceuticals, Inc.	402-C-319

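### AESI status is described inconsistently and the SAP names no source for its AESI incidence tables, so the incidence could depend on unblinded attribution

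*Protocol*

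**What the plan says.** Three descriptions of an AESI sit side by side.

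- **An event list.** Protocol 13.1.7 states: "Cardiac AESIs include chest pain, abnormal/irregular heart rate, and shortness of breath requiring intervention". A parallel neurological list covers seizure, tremors, tinnitus and others. For dizziness, hyperesthesia, twitching and tingling/paresthesia it adds that "the following events may be of special interest if they persist or occur beyond 72 hours post dose". No causal condition is attached. The synopsis, Section 9.1, Table 1 footnote 7 and SAP Section 3 carry the same list.
- **Three conditions.** Under Protocol 9.1, once an AESI or SAE has occurred, an unscheduled PK sample is required "if the investigator or medical monitor considers that the event may be related to study treatment", or if the event "suggests the possible occurrence of local anesthetic systemic toxicity", or if no plausible cause is found. After a cross-reference the text continues: "Cardiac or neurological AEs that do not meet one of these three criteria for AESI should be reported as described in Section 14.1". SAP Section 3 places its version directly after the same trigger: "Cardiac and neurological AEs that do not meet one of these three criteria for AESI should be reported and captured in the database as an" (the sentence ends by classing such an event as an ordinary AE).
- **A shorthand.** Table 1 footnotes 1 and 4 allow an extra ECG or vital signs "if a subject experiences an AESI (i.e., cardiac AE or neurological AE), or an SAE". SAP Section 9 copies these footnotes.

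For analysis, SAP Table 5 (Section 6.8.4) maps the protocol list to MedDRA preferred terms with no relatedness condition. It adds that investigators report according to this definition and their clinical judgement. For Listings 16.2-17.5.1.1.x the SAP instructs: "For these tables, use the CRF checkbox to identify AEs of Special Interest". Listings 16.2-17.5.3.1.x use Table 5 instead. Neither source is named for the AESI row of the TEAE overview or for Tables 14.3-6.1.x, the AESI incidence tables.

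**The concern.** The three descriptions cover different sets of events. The sentence in Protocol 9.1 and SAP Section 3, taken literally, turns a rule about when to draw blood into a rule about what counts as an AESI. Under that rule a listed event is left out when it is judged unrelated, does not suggest systemic toxicity, and has another explanation. In this trial other explanations will be at hand, because intraoperative opioids are permitted and every child has just had spine or cardiac surgery.

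Safety is the secondary objective and the purpose of Part 2. The study is open-label, so in randomized Group 1 the person judging cause knows the arm. With the source unstated, two programmers could also produce different AESI incidences from the same data.

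**Working it through.** The plan gives no AESI rate, so there is no figure to reproduce. The first check is textual.

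**Step 1: what the 'three criteria' sentence follows in each place**

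| Place | Sentence follows | Calls them criteria for an AESI? |
|---|---|---|
| Protocol 9.1 | PK-sample trigger, after a cross-reference | Yes |
| SAP Section 3 | PK-sample trigger, directly | Yes |
| Table 1 footnote 7, and its copy in SAP Section 9 | PK-sample trigger, after a cross-reference | No |
| Synopsis and Protocol 13.1.7 | Event lists and the dizziness rule | Yes |

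In Protocol 9.1 and SAP Section 3 the only preceding set of three is the trigger. The result is circular: the trigger applies to an AESI that has already occurred, and its conditions are then called the criteria for being one. In the synopsis and 13.1.7 the antecedent is unclear.

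**Step 2: one case through each rule.** Take a tremor that is put down to opioids, judged unrelated to study drug and not suggestive of systemic toxicity.

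- Event list: AESI.
- Table 5: AESI (Tremor is a listed preferred term).
- Footnotes 1 and 4: AESI.
- Protocol 9.1 and SAP Section 3, read literally: plain AE.
- CRF checkbox: depends on which text the site followed.

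**Step 3: what the literal reading could do to a count.** This is an illustration; the rates are assumptions.

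- n = 30 per Group 1 arm, from 15 per arm in each of two parts (2 x 15).
- p = true proportion of children with a listed event, assumed equal in both arms.
- q = proportion of those whose event meets one of the three conditions.
- Expected count on the event list = n x p. Expected count under the literal reading = n x p x q. Apparent difference = p x (q1 - q2).

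With q1 = 0.8 and q2 = 0.4:

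| p | Event list, each arm | Literal reading, arm 1 vs arm 2 | Apparent difference |
|---|---|---|---|
| 10% | 3.0 | 2.4 vs 1.2 (8% vs 4%) | 4 points |
| 20% | 6.0 | 4.8 vs 2.4 (16% vs 8%) | 8 points |
| 30% | 9.0 | 7.2 vs 3.6 (24% vs 12%) | 12 points |
| 40% | 12.0 | 9.6 vs 4.8 (32% vs 16%) | 16 points |

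Exchanging q1 and q2 reverses the sign. With q = 0.5 in both arms the difference is 0, but each incidence is halved (at p = 20%, 3 instead of 6 of 30). At p = 20%, q from 0.1 to 0.5 gives 0.6 to 3 of 30 (2% to 10%) instead of 6 of 30 (20%). Event-based counting gives a difference of 0 at every p.

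**The case against.** The case on the other side is substantial.

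- **The SAP already holds an event-based definition.** Table 5 has no causal filter, and the listings titled as protocol-defined use it. A reader might infer that AESI incidence here depends on attribution and not on the event. The documents do not support that, since only the investigator-reported listings are expressly tied to the checkbox.
- **The attribution reading is contestable.** The trigger presupposes an AESI. Protocol Section 14 points to 13.1.7 for the description of AESIs, and there the sentence follows the event lists and the dizziness rule. The three criteria could be the three lists, which would match Table 5's three groups (Cardiac, Neurologic, Other). This weakens the literal reading of 9.1 but does not remove it, because in 9.1 and SAP Section 3 the lists come only afterwards. The three dizziness limbs are a poor antecedent, since chest pain or seizure cannot be tested against them.
- **The footnotes are loose shorthand.** They concern optional procedures and refer to footnote 7, which gives the list. This stands; they need tidying but are not a competing counting rule.
- **The consequences are bounded.** Protocol 12.4 lists incidence of TEAEs and SAEs, not of AESIs, and no test of AESIs is planned. An event not classed as an AESI is still recorded and, if treatment-emergent, tabulated. SAP 6.8.3 also tabulates neurological findings without attribution. All of this stands.
- **Direction is unknown.** A reader might infer a bias for or against EXPAREL. Both arms receive bupivacaine, the medical monitor may also judge relatedness, and suspected toxicity is a separate route, so no direction can be claimed.
- **Some material cannot be read here.** The Appendix 6 flow diagram and the CRF might clarify site practice. The text cites Appendix 6 for handling AESIs, not for defining them.

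**Conclusion.** The inconsistency is real and should be corrected. It is more than missing detail, because a stated rule in Protocol 9.1 and SAP Section 3 would, read literally, declassify events that the protocol itself lists as AESIs. The SAP leaves open whether its AESI incidence uses the checkbox or Table 5.

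Dependence on attribution is conditional. It requires both that the checkbox feeds the overview row and Tables 14.3-6.1.x, and that sites apply the 9.1 wording. Its size and its direction by arm are unknown. The 4 to 16 point range rests entirely on the assumed rates and shows only that arms of 30 are sensitive: one child is 1/30 = 3.3 points. The effect is confined to descriptive AESI displays.

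**What to change.** **Protocol.** Reconcile the synopsis, Table 1 footnotes 1, 4 and 7, and Sections 9.1 and 13.1.7, so that AESI status for reporting and analysis rests on the existing event list. Keep this separate from the triggers for additional procedures, which stay as they are. For example, delete the words 'for AESI' after the three criteria in 9.1, make the antecedent clear in the synopsis and 13.1.7, and remove the 'i.e.' gloss from footnotes 1 and 4.

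**SAP.** Make the matching changes in Section 3 and in the Section 9 copies of the footnotes. State that the AESI row of the TEAE overview and Tables 14.3-6.1.x count the protocol-listed events (Table 5, applied with the protocol's time and severity qualifiers) regardless of causality. Show the investigator-flagged subset as a separate row.

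**Cost.** Wording changes, a CRF completion note and one extra table row. Both sources are already planned for the listings, so no new data are needed. The reported AESI incidence may be higher than under a narrower count.
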